### **8.1.3 Unexpected AE or SAR**

An AE or SAR is considered unexpected if the specificity or severity of it is not consistent with the applicable product information (e.g., package insert/summary of product characteristics for an approved product). Unexpected also refers to AEs or SARs that are mentioned in the IB as occurring with a class of drugs or as anticipated from the pharmacological properties of the drug, but are not specifically mentioned as occurring with the particular drug under investigation.

### **8.1.4 Serious AE or SAR**

An AE or SAR is considered serious if, in the view of either the investigator or sponsor, it results in any of the following outcomes:

- Death;
- Is life-threatening (places the participant at immediate risk of death from the event as it occurred);
- Requires inpatient hospitalization (>24 hours) or prolongation of existing hospitalization;\*
- Results in congenital anomaly/birth defect;

- Results in a persistent or significant incapacity or substantial disruption of the ability to conduct normal life functions;
- Important medical events that may not result in death, be life-threatening, or require hospitalization may be considered a serious adverse drug experience when, based upon appropriate medical judgment, they may jeopardize the patient or participant and may require medical or surgical intervention to prevent one of the outcomes listed in the definition. For reporting purposes, also consider the occurrences of pregnancy as an event which must be reported as an important medical event.

\*Hospitalization for anticipated or protocol specified procedures such as administration of chemotherapy, central line insertion, metastasis interventional therapy, resection of primary tumor, or elective surgery, will not be considered serious adverse events.

Pregnancy that occurs during the study must also be reported as an SAE.

## **8.2 Documentation of non-serious AEs or SARs**

For non-serious AEs or SARs, documentation must begin from day 1 of study treatment and continue through the 30 day follow-up period after treatment is discontinued.

Collected information should be recorded in the Case Report Forms (CRF) for that patient. Please include a description of the event, its severity or toxicity grade, onset and resolved dates (if applicable), and the relationship to the study drug. Documentation should occur at least monthly.

## **8.3 SAEs or Serious SARs**

### **8.3.1 Timing**

After informed consent but prior to initiation of study medications, only SAEs caused by a protocol-mandated intervention will be collected (e.g. SAEs related to invasive procedures such as biopsies, medication washout).

For any other experience or condition that meets the definition of an SAE or a serious SAR, recording of the event must begin from day 1 of study treatment and continue through the 30 day follow-up period after treatment is discontinued.

### **8.3.2 Documentation and Notification**

SAEs or Serious SARs must be recorded in the SAE console within Oncore™ for that patient within 24 hours of learning of its occurrence. Additionally, the NCCN Project Manager must also be notified via email of all SAEs within 24 hours of learning of its occurrence.

## 8.4 Adverse Event Reporting

### 8.4.1 IRB Reporting Requirements:

UNC:

- The UNC-IRB will be notified of all SAEs that qualify as an Unanticipated Problem as per the UNC IRB Policies using the IRB's web-based reporting system (see section 10.4.3) within 7 days of the Investigator becoming aware of the problem.

### 8.4.2 Funding Source (e.g. Manufacturer) Reporting Requirements:

N/A

## 8.5 Data and Safety Monitoring Plan

This is a Phase II, single site study of 56 individuals to gather preliminary data on the efficacy and feasibility of memantine in patients with breast cancer receiving chemotherapy. We will follow our standard protocol for monitoring of clinical trials. Participants are screened to ensure that there are no contraindications to their participation.

The study PI, [name], will be responsible for continuous monitoring of patient safety during the trial. For non-serious Adverse Events (AEs), documentation will begin from the first day of study treatment and continue through the 30-day follow-up period after treatment is discontinued. Collected information will be recorded in Case Report Forms (CRF) for that patient. A description of the event, its severity or toxicity grade, onset and resolved dates (if applicable), and the relationship to the study drug will be included. For any experience or condition that meets the definition of a serious adverse event (SAE), recording of the event will begin after signing of the informed consent and continue through the 30-day follow-up period after treatment is discontinued. These events will be recorded in the CRF for that patient within 24 hours of learning of its occurrence. If the event is both serious AND unexpected, it will also be recorded on the MedWatch Form 3500A, as per 21 CFR 312.32, and forwarded to the FDA in accordance with 21 CFR 314.80 (for marketed drugs). The UNC IRB will be notified of all SAEs that qualify as an Unanticipated Problem (serious, unexpected, and related) as per the UNC IRB policies. In accordance with these policies, an aggregated list of all SAEs will be submitted to the UNC IRB annually at the time of study renewal.

Periodic review, at an interval of every six months to annually, by the Lineberger Comprehensive Cancer Center Data Safety Committee (LCCC DSMC), Protocol Review Committee (PRC), and Office of Human Research Ethics (OHRE) Biomedical IRB will provide oversight of the PI's continuous monitoring. For each DSMC review, summary information regarding toxicity and accrual patterns will be prepared and submitted by the PI. Specific information submitted for review includes: (1) The number of patients enrolled, consented, consented but not treated, currently being treated, completed treatment, the number of patients who did not complete treatment and the reasons for coming off study; (2) Grade 3 or greater reported Adverse Events to date; (3) Serious

Adverse Events and Unanticipated Problems since last report, with assurance of reporting to internal and external regulating bodies; (4) Exceptions in eligibility or treatment and significant protocol deviations/violations; (5) Significant literature reporting developments that may affect the safety of participants or the ethics of the study; (6) Summaries of team meetings that have occurred since the last report; (7) Results of interim analyses required by the protocol. We will also be submitting a preliminary report of response and other endpoints listed in the primary and secondary objectives of the protocol for DSMC review.

Though no formal *a priori* stopping rules are proposed for the study, in the event of a serious or unexpected adverse event or frequent occurrence of less serious unexpected or expected adverse events we will consult with the OHRE and DSMC as to whether the trial should continue.

## 9.0 STATISTICAL CONSIDERATIONS

### 9.1 Study Design/Study Endpoints

This is a one-arm interventional pilot study in participants receiving chemotherapy for breast cancer to evaluate if memantine can prevent cognitive decline. We will recruit 56 patients from the UNC Breast, Hillsborough Oncology, and UNC REX Cancer Center clinics, treat with memantine 10 mg twice daily, and systematically evaluate cognitive function, mental health, HRQOL, and functional status at baseline and at the end of chemotherapy (and again at 6 months post-chemotherapy in a subset of participants). We will also serially assess tolerability of and adherence with memantine.

The primary efficacy endpoint is cognitive decline measured as a change in DMS score. Scores range from 0-100%, defined by the percent of correct answers on the memory test. Secondary endpoints include other measures of cognitive function (HVLT-R, RVP, OTS, Digit Span, COWA, ANT, and PROMIS Cognitive Function), depression, anxiety, HRQOL, and functional status. The TMT-A and -B will also be evaluated as secondary endpoints in the subset of participants who completed the study prior to the removal of these measures.

### 9.2 Sample Size, Accrual and Duration of Accrual

Though chemotherapy is known to result in cognitive decline, the study by Janelsins reports a 5% increase in scores on the DMS (83% to 88%) in patients with breast cancer from pre-to post-chemotherapy. An increase in score in spite of cognitive decline is consistent with the well-described phenomena of practice effects in both healthy and cancer populations with repeat neuropsychological testing. In our sample exposed to memantine, we hypothesize that our sample will have an 8% increase in the DMS score as compared to the 5% increase in breast cancer controls described in Janelsins study.

For the primary objective of cognitive change, a paired t-test with a 0.05 one-sided significance level will have 80% power to detect an effect size of 0.376 with a sample size of 45. Specifically, patients with breast cancer demonstrate a 5% increase in the DMS pre- to post- chemotherapy; thus, 5% is the null hypothesized change. The alternative hypothesis is that patients receiving memantine will experience less chemotherapy-related cognitive decline, and will have an 8% increase. Using these hypothesized values, in combination with sample size budgetary constraints, we chose the final sample size of 45. With 45 patients, we will have 80% power to test if the change scores in our study population are significantly different than the historical control data reported by Janelsins (assuming a 3% mean increase, and standard deviation of the increase of 7.97%). This study will provide preliminary data and effect sizes to power a future, larger placebo-controlled study.

To account for dropout of up to 20%, we will enroll 56 participants. The UNC Cancer Registry records demonstrate that 537 stage I-III breast cancer patients were referred to the NC Cancer Hospital for chemotherapy between 2016 and 2017. We estimate that we will enroll at least 33% of eligible participants, based on our experience with previous intervention studies, allowing us to recruit our target within one year.

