## 3.0 **Criteria for Evaluation / Study Endpoints**

### 3.1 **Primary Endpoint**

The primary endpoint is change in the pre- to post-chemotherapy DMS score. The DMS will be quantified as percent correct at 12-second delay.

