### OBJECTIVE COGNITIVE FUNCTION MEASURES

#### 5.8.1 Delayed Matching to Sample Test (DMS)

The Delayed Matching to Sample Test (DMS) is a computerized cognitive assessment of visual working memory. The DMS will be administered using CANTAB eclipse software (Cambridge Cognition, Cambridge, UK). The participant is shown an image with four patterns and asked to match patterns simultaneously or after delay. We will use the percent correct at the 12-second delay on the DMS test for the primary analysis. The DMS will take 7 minutes to complete. All participants who are enrolled in the trial will be evaluated pre- and post-chemotherapy.

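### Is the 80% power in section 9.2 undermined because its one SD of change, 7.97 points, has no clear source and is not tied to the 12-second score?

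*Combined protocol and SAP*

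**What the plan says.** Section 9.2 takes its null value from a published cohort which, it says, "reports a 5% increase in scores on the DMS (83% to 88%) in patients with breast cancer". The alternative is that "patients receiving memantine will experience less chemotherapy-related cognitive decline, and will have an 8% increase". A paired t-test at one-sided 0.05 "will have 80% power to detect an effect size of 0.376 with a sample size of 45". The same power is then given in raw units, "assuming a 3% mean increase, and standard deviation of the increase of 7.97" percent. On the number itself, the hypothesised values were used "in combination with sample size budgetary constraints, we chose the final sample size of 45". The section closes on purpose: "This study will provide preliminary data and effect sizes to power a future, larger placebo-controlled study".

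Section 3.1 defines the endpoint: "The DMS will be quantified as percent correct at 12-second delay". Section 5.8.1 repeats this: "We will use the percent correct at the 12-second delay on the DMS test for the primary analysis". It also gives 7 minutes for the whole DMS. Appendix A shows that the test contains simultaneous and 4-second trials as well as 12-second ones. Section 9.1 describes the score only as a percentage of correct answers from 0 to 100. No other SD, correlation or sensitivity range appears in the protocol.

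**The concern.** Three features invite suspicion.

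- **Source.** The SD stands in a bracket just after a mention of the historical data. A reader cannot tell whether the cohort reported it, whether it was derived, or whether it was chosen. To the printed decimals it equals the SD that makes n = 45 give exactly 80% power for 3 points.
- **Score.** A 12-second score uses only some of the test's trials, so it should be noisier than a score over all delays. Section 9.2 does not say which of the two the 83%, 88% and 7.97% describe.
- **Sensitivity.** Only one SD is shown, and power for 3 points falls quickly as the SD grows.

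If the true SD were well above 7.97, a non-significant primary test would be credited with more power than it had. That could wrongly discourage the larger placebo-controlled trial, or lead to that trial being planned on too small an SD.

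**Working it through.** **Inputs.** From section 9.2: n = 45, one-sided alpha 0.05, null change 5, alternative 8, SD of change 7.97. From section 5.8.1: 7 minutes = 420 s. From Appendix A: delays of 0, 4 and 12 s. The number of 12-second trials, k, is not given and has to be assumed.

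**1. The plan's own figure.** The paired test against a fixed 5 is a one-sample t-test on the change scores.

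- Effect size: d = (8 − 5)/7.97 = 0.3764.
- Noncentrality: 0.3764 × √45 = 2.525; critical t on 44 df = 1.680.
- Exact power: 0.7998.

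The stated 80% reproduces.

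**2. Back-solving.** The d that gives exactly 80% at n = 45 is 0.3765, and 3/0.3765 = 7.968, which rounds to 7.97. This fits a design in which n was fixed first. It neither proves that nor shows the SD to be wrong.

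**3. Sensitivity to the SD** (n = 45, 3 points, one-sided 0.05; every SD except 7.97 is an assumption).

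| SD of change | Power for 3 points | Difference detectable with 80% power (0.3765 × SD) |
|---|---|---|
| 7.97 | 80% | 3.0 |
| 8.5 | 75% | 3.2 |
| 9 | 71% | 3.4 |
| 10 | 63% | 3.8 |
| 12 | 50% | 4.5 |
| 15 | 37% | 5.6 |

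**4. Can the documents show that 7.97 is too small?** Suppose answers are independent, all items are equally hard, and true change does not vary between patients. Then

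SD = 100 × √[(p₁(1 − p₁) + p₂(1 − p₂))/k].

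- For 83% then 88%: 0.1411 + 0.1056 = 0.2467. SD 7.97 needs k = 0.2467/0.0797² = 38.8.
- For 83% then 91%: 0.1411 + 0.0819 = 0.2230, so k = 35.1.
- The delays alone would take 35 × 12 = 420 s to 39 × 12 = 468 s, which is the whole test or more.
- With equal numbers of the three delays and no display or response time, k is at most 420/16 = 26. At k = 26 with 83% then 88%, SD = 9.74 and power is 65%.

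This looks damaging, but the answer moves with each assumption:

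- Letting items and patients differ (item logit SD 0 to 2, person logit SD 0 or 0.8, either pair of means) gives SD 7.52 to 9.74 and power 65% to 84% at k = 26.
- Allowing 2 s of handling per trial gives k = 420/(16 + 6) = 19, SD 8.80 to 11.39 and power 54% to 73%.
- Variation in true change with an SD of 3 points lowers the upper end at k = 26 to 79%.
- If a patient's answers to the same item are correlated before and after, the SD shrinks. The most favourable case at k = 20 has SD 8.58 and power 75%. With correlation 0.15 the SD is about 8.58 × √0.85 = 7.91 (power about 80%); with 0.30 it is about 8.58 × √0.70 = 7.18 (about 87%).

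The check leans towards a larger SD but does not exclude 7.97.

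**The case for a change.** The strongest case for a change needs no modelling. The power for 3 points rests on one number that a reader cannot trace. That number coincides with the back-solved value, and nothing ties it to the score the trial will analyse. A rise of about one point in the SD, from 7.97 to 9, costs about 9 points of power (80% to 71%). The repair would be a few lines of text, and the trial exists to inform a later one.

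The factual part stands: source, range and link to the 12-second score are all absent. Three things weaken the step from there to a defect.

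- The bracket opens with an assumption, and that wording also covers a 3% increase. That cannot be the cohort's reported change, which is 5%, so the natural reading is a list of design assumptions. With budget named as a reason for 45, the match to 7.968 reflects an openly constrained design.
- The first power statement is standardised. Power of 80% for an effect of 0.376 with 45 patients is true whatever the SD; only the translation into 3 points depends on 7.97.
- Sections 3.1 and 5.8.1 fix how the DMS is scored. Section 9.1 can be read as describing the scale, without setting up a rival all-delay score. Whether the cohort's figures are 12-second values depends on the cited paper, which is not among the documents.

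Computing a replacement SD from the number of trials would not be sound either, because that counts chance error only and leaves out variation in true change.

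**Conclusion.** The concern does not call for a change. The stated 80% is correct for its stated inputs (79.98%), and no figure in the plan is shown to be wrong. The SD of 7.97 may be optimistic for a 12-second score. Saying so with confidence requires a trial count the documents do not give, an assumed equal mix of delays, 7 minutes taken as a hard limit, and independent answers before and after chemotherapy. Within that model the power at 26 trials is 65% to 84%, so the plan's figure is not excluded.

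What remains is missing detail in a sample size rationale for a pilot whose number was partly set by budget. Supplying it would leave enrolment, endpoint, test and decision rule as they are. The trial will observe its own SD of change, which is what a reader of a non-significant result, or the planner of the next trial, should use in place of the planning value. Until then, the rule 0.3765 × SD converts the standardised statement into points for any SD a reader finds plausible, for example 3.4 points at SD 9 and 4.5 at SD 12.

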### 9.3 Data Analysis Plans

The primary outcome is change in the DMS score. A paired t-test will test if the change in DMS score from pre- to post-chemotherapy is statistically different from historical controls. Pre- to post-chemotherapy, as well as pre- to 6 months post-chemotherapy, changes in all other cognitive measures will also be evaluated using paired t-tests.

Linear regression models will be used to cross-sectionally evaluate associations between depression (PROMIS-D), anxiety (PROMIS-A), sleep (PROMIS-Sleep Disturbance), menopausal status, fatigue (FACIT-F), estimated pre-cancer IQ (WTAR), and cognitive effort (NASA-TLX) with both objective (DMS, HVLT-R, COWA, ANT, Digit Span) and self-reported (PROMIS) measures of cognitive function at baseline and post-chemotherapy. Linear mixed effects models will evaluate associations across pre- and post- time points.

Linear regression modeling will describe the associations between pre- to post-chemotherapy cognitive changes (DMS, HVLT-R, COWA, ANT, Digit Span, PROMIS) with post-chemotherapy depression and anxiety (PROMIS), HRQOL (FACT-G), and performance status (KPS).

Descriptive statistics will be used to estimate feasibility: 1.) recruitment rate (% of invited participants who enroll), 2.) attrition (% of enrolled participants who are not eligible for analysis of the primary outcome), and 3.) adherence to treatment (% self-reported doses of memantine taken).

We will tabulate all AEs, the dose at which they occurred, and if they led to dosing delays or removal from the study.

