### 2.2 **Secondary Objectives**

**2.2.1** To compare pre- to post-chemotherapy changes in all other objective and self-reported cognitive function measures.

**2.2.2** To examine associations between objective and self-reported cognitive function with depression, anxiety, fatigue, menopausal status, baseline IQ, and perceived cognitive effort, cross-sectionally pre- and post-chemotherapy.

**2.2.3** To explore the impact of cognitive decline on health-related quality of life (HRQOL), functional status, depression, and anxiety.

**2.2.4** To estimate the feasibility of conducting a clinical trial of memantine for attenuating cognitive decline in patients with breast cancer during chemotherapy.

**2.2.5** To describe the safety of administering memantine to patients with breast cancer during chemotherapy.

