### **3.2 Secondary Endpoints**

**3.2.1** Changes in other objective (HVLT-R, RVP, OTS, Digit Span, COWA, Animal Naming Test) and self-reported (PROMIS Cognitive Function) cognitive measures will be measured from pre- to post-chemotherapy.

**3.2.2** Depression (PROMIS-Depression), Anxiety (PROMIS-Anxiety), fatigue (Functional Assessment of Chronic Illness Therapy – Fatigue, FACIT-F), menopausal status (Hormonal Status Questionnaire and follicle stimulating hormone level, FSH), and perceived cognitive effort (NASA-Task Load Index, NASA-TLX) will be measured pre- and post-chemotherapy. Baseline IQ (Wechsler Adult Test of Reading, WTAR) will be measured pre-chemotherapy only.

**3.2.3** Health-related quality of life (Functional Assessment of Cancer Therapy – General, FACT-G) and functional status (Patient-reported Karnofsky Performance Status, Patient-KPS) will be measured pre- and post-chemotherapy.

**3.2.4** Recruitment will be measured as proportion of approached participants who agree to enroll and number of participants enrolled per month. Retention will be measured as proportion of enrolled participants who complete the primary outcome measure pre- and post-chemotherapy. Adherence will be measured as patient-reported proportion of prescribed doses of memantine actually taken.

**3.2.5** Safety will be measured as the frequency of reported adverse events (AEs).

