### **5.8.12 Patient Reported Outcomes Measurement Information System – Depression (PROMIS-D)**

The National Institute of Health's Patient-Reported Outcomes Measurement Information System (PROMIS) contains a depression bank. We will use the PROMIS Depression 8a short form. Higher scores represent greater degrees of depression. The PROMIS-D will take less than 2 minutes to complete. All participants who are enrolled in the trial will be evaluated pre- and post-chemotherapy.

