### **5.8.13 Patient Reported Outcomes Measurement Information System – Anxiety (PROMIS-A)**

The National Institute of Health's Patient-Reported Outcomes Measurement Information System (PROMIS) contains an anxiety bank. We will use the PROMIS Emotional Distress-Anxiety – Short Form 6a. Higher scores represent greater degrees of anxiety. The PROMIS Anxiety will take less than 2 minutes to complete. All participants who are enrolled in the trial will be evaluated pre- and post-chemotherapy.

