#### **5.8.16 Patient-Reported Karnofsky Performance Status (Patient-KPS)**

The Patient-reported KPS provides a self-characterization of functional status, ranging from severely/require continuous nursing care to normal/no complaints/no symptoms of disease. Scores range from 30 to 100. Higher scores indicate better function. The Patient-KPS will take less than 2 minutes to complete. All participants who are enrolled in the trial will be evaluated pre- and post-chemotherapy.

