#### **5.8.17 Functional Assessment of Cancer Therapy-General (FACT-G)**

The FACT-G is a 27-item patient-administered assessment of general quality-of-life measures in cancer patients. It has been validated in the literature and permits the measurement of a number of symptoms including nausea, pain, and insomnia. The FACT-G will take no greater than 5 minutes to complete. All participants who are enrolled in the trial will be evaluated pre- and post-chemotherapy.

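### For exploratory objective 2.2.3, section 9.3 models post-chemotherapy mood, quality of life and function without their baseline values, although all four baselines are collected: a minor, low-cost improvement

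*Combined protocol and SAP*

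**What the plan says.** Objective 2.2.3 (section 2.2) reads: "To explore the impact of cognitive decline on health-related quality of life (HRQOL), functional status, depression, and anxiety". The only sentence in section 9.3 that covers all four of these outcomes says linear regression will describe associations of pre- to post-chemotherapy "cognitive changes (DMS, HVLT-R, COWA, ANT, Digit Span, PROMIS) with post-chemotherapy depression and anxiety", then adds FACT-G and KPS. The outcomes enter at their post-chemotherapy level. The sentence names no baseline value, no change score in the outcomes and no covariate.

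All four baselines are scheduled for every participant:
- **PROMIS-Depression**, section 5.8.12: "The PROMIS-D will take less than 2 minutes to complete. All participants who are enrolled in the trial will be evaluated pre- and post-chemotherapy".
- **PROMIS-Anxiety**, section 5.8.13 and the Time and Events Table in 7.1: same two visits.
- **Patient-KPS**, section 3.2.3: "functional status (Patient-reported Karnofsky Performance Status, Patient-KPS) will be measured pre- and post-chemotherapy"; section 5.8.16 agrees.
- **FACT-G**, section 5.8.17: "All participants who are enrolled in the trial will be evaluated pre- and post-chemotherapy".

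The nearest text that might supply a baseline is the sentence in 9.3 that "Linear mixed effects models will evaluate associations across pre- and post- time points". It closes the preceding paragraph, which serves objective 2.2.2. The correlates listed there include depression and anxiety, but not FACT-G or KPS. The synopsis (1.1) names depression and anxiety among covariates because they affect cognition. It mentions quality of life and functional status only as outcomes.

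**The concern.** A patient's mood, quality of life or function after chemotherapy depends partly on where she started. If the starting value is also related to how much her cognition changes, a regression of the later value on cognitive change carries both things in one slope. The protocol makes such a relation plausible: section 1.1 treats depression and anxiety as affecting cognition. Section 1.2 notes the criticism that self-reported cognition may reflect depression, anxiety or fatigue, and PROMIS cognitive change is one of the six predictors. If the starting value is unrelated to cognitive change, leaving it out causes no bias but discards available precision. What is at stake is how results reported under objective 2.2.3 can be read. The primary comparison is not involved.

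**Working it through.** **Figures in the plan.** Section 9.2 gives no power or precision for these regressions. Its primary-endpoint figure reproduces: 3/7.97 = 0.376, and the exact one-sided 5% t-test power at n = 45 is 0.7998, against 80% stated. It serves here only as the source of n = 45.

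**Assumed inputs (none is in the documents).** All variables are standardised.
- Y0, Y1: outcome before and after. C0, C1: cognition before and after.
- corr(C0, C1) = 0.5, so var(C1 − C0) = 1 + 1 − 2 × 0.5 = 1.
- r: carry-over of the outcome from Y0 to Y1 (its pre-post correlation when cognitive change has no effect), 0.3 to 0.7.
- g: correlation of Y0 with cognitive change.
- b: slope of interest, −0.30 or 0. d: direct effect of C0 on Y1.
- Model: Y1 = r·Y0 + d·C0 + b·(C1 − C0) + e, with SD(e) = √(1 − r²). Each setting has 20,000 simulated trials of n = 45, tested two-sided at 5%.

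**Precision, g = 0, d = 0, b = −0.30.** At r = 0.6 the standard error (SE) is about 1/√43 = 0.152 unadjusted and √(1 − 0.36)/√42 = 0.8/√42 = 0.123 with Y0 added. The ratio is 0.81, a fall of about 19%. The 95% CI half-width goes from 0.31 to 0.25.

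| r | SE unadjusted | SE + Y0 | change | SE + Y0 + C0 |
|---|---|---|---|---|
| 0.3 | 0.152 | 0.147 | −3% | 0.172 |
| 0.4 | 0.152 | 0.141 | −7% | 0.165 |
| 0.5 | 0.152 | 0.134 | −12% | 0.156 |
| 0.6 | 0.152 | 0.123 | −19% | 0.144 |
| 0.7 | 0.152 | 0.110 | −28% | 0.129 |

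**Precision when g is not 0.** The large-sample SE ratio, adjusted to unadjusted, is √[(1 − r²) / ((1 − g²)(1 − r²g²))]. It equals 1 at g = 0.29 for r = 0.3 and at g = 0.61 for r = 0.7. In simulation with g = 0.4 the SE changes by +6%, +2.5%, −2%, −9% and −18% for r = 0.3 to 0.7.

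**Bias from omitting Y0 (d = 0).** The unadjusted slope is b + r·g.
- Suppose baseline mood relates to later cognition only through C0, with corr(Y0, C0) = ρ. Then g = 0.5ρ − ρ = −0.5ρ. At r = 0.6, ρ = −0.2 gives −0.30 + 0.6 × 0.1 = −0.24, and ρ = −0.4 gives −0.30 + 0.6 × 0.2 = −0.18. Simulated: −0.241 and −0.182. With Y0 added the slope is −0.30.
- If Y0 has the same correlation with cognition at both visits, g = ρ − ρ = 0 and neither slope is biased.
- With g set directly and b = 0, nominal 5% rejection without Y0 becomes 8% to 19% at g = −0.2 and 12% to 36% at g = −0.3 (r from 0.4 to 0.8). With Y0 it stays near 5%.

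**Where adding Y0 alone does not help.** If C0 acts directly on Y1, b = 0 and Y0 is unrelated to cognition, the slope becomes d × (0.5 − 1) = −0.5d, with or without Y0. For d = −0.3 it is +0.15 either way. Because the SE is smaller, false rejection rises from 15.4% to 20.2% when Y0 is added (r = 0.6). Adding C0 returns the slope to 0 and rejection to 5.0%.

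**The case against.** The strongest reply concerns weight. The objective is secondary and exploratory, the regressions are descriptive, and no test, power or causal claim rests on them. An unadjusted association is a legitimate descriptive quantity, and 9.3 does not say that the models must be univariable. All of that stands, and it makes this an improvement to the plan and not an error in it.

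The reply can also point to the covariate wording in 1.1 and to the group heading above 5.8.11, which covers covariates and secondary outcomes together. Neither places an outcome's own baseline in the 2.2.3 models, so the gap remains.

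A reader might infer that, as planned, patients who began with worse mood cannot be told apart at all from those affected by decline. The documents do not support that. For depression and anxiety, 9.3 also plans baseline cross-sectional regressions and mixed models across visits, although with cognition as the response. The omission is complete only for FACT-G and KPS. A reader might also infer that the planned intervals will usually be too wide. That depends on r and g, which the documents do not give, and the sign of the precision effect can reverse.

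Finally, no adjusted model is best under every structure. Adding the baseline outcome alone can worsen false rejection when baseline cognition acts directly, and adding baseline cognition costs precision. This is why the planned model should stay and the adjusted ones be reported beside it.

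**Conclusion.** The point holds as a minor, low-cost improvement. Section 9.3 relates cognitive change to the post-chemotherapy level of four outcomes without their baselines, and all four baselines are collected. Depending on whether an outcome's baseline is correlated with cognitive change, the planned slope either mixes in pre-existing mood, quality of life or function, or is less precise than it could be.

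Every size shown rests on assumed correlations at n = 45. The SE falls about 19% at r = 0.6 and g = 0, and rises a few percent at low r and high g. There is no bias from the omitted baseline when g = 0.

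A reader might take the adjusted slope as showing the impact of decline. It would not: section 7.4 measures cognition and these outcomes at the same post-chemotherapy visit, so the direction of effect stays open under any of these models. The primary test, the 45 analysable patients and the enrolment of 56 are unaffected.

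**What to change.** Keep the planned regressions and their six named cognitive measures, and add to 9.3:

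> For each cognitive measure listed above and each outcome (PROMIS-D, PROMIS-A, FACT-G, KPS), the model will also be fitted with the baseline value of that outcome as a covariate and reported beside the unadjusted model, with slopes and 95% confidence intervals, as exploratory. A sensitivity model will also include the baseline score of the cognitive measure.

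No new data, visits or patients are needed. The costs are:
- **Degrees of freedom:** one per baseline-adjusted model, two per sensitivity model.
- **Output:** counting one score per measure, 6 × 4 = 24 models become 48, or 72 with the sensitivity model, all exploratory.
- **Precision of the sensitivity model:** under the assumptions above with g = 0, its SE is about 17% larger than with the baseline outcome alone (0.144 against 0.123 at r = 0.6; power 54% against 67%). It also exceeds the unadjusted SE at r of 0.5 or lower (+3% at 0.5, +13% at 0.3).

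The report should say that the baseline-outcome model does not remove bias from a direct effect of baseline cognition, so that the models are read together.
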